### F. Risks and Side Effects:

There are various possible risks and side effects that a participant may incur as a result of this study. At the beginning of the study, when participants are administered the informed consent form by research staff, they will be informed that their participation is completely voluntary and will be informed of the risks and benefits. They are free to leave the study at any time and will not be penalized. Potential subjects will also be told that failure to participate in no way affects the usual care they would receive from their primary care provider. Only after all questions have been answered, both study staff and the participant will sign and date the consent form.

It is very unlikely that there will be any adverse event from the lifestyle intervention except possible musculoskeletal injury from increased physical activity, but this will be mitigated as participants will be taught how to gradually increase their activity goals. Typically, musculoskeletal soreness and discomfort is minimal and temporary. The risks associated with exercise occur occasionally (1-10% or 1-10 people in 100) and include fatigue, muscle soreness, and injury such as sprained ankles or pulled muscles (39). Risks are reduced by proper warm-up and cool-down periods.

There may be additional risk of heart problems for those who have a chronic disease or experience symptoms with exercise, although this risk is extremely minimal given the intensity of the recommended exercise, i.e., brisk walking or jogging in a young population. The level of activity that we will recommend for participants is thought to be more helpful than harmful, but there is a very small risk of heart attack or sudden death during exercise. Heart attack has been estimated to occur less than once out of 500,000 hours of exercise in people without known heart disease (40). The risk is greater in people with heart disease. It is important that participants contact their physician if they develop diabetes, heart disease or other related health problems during this study.

Modest weight loss is also associated with a few risks. It is common or likely for participants to experience hunger, lightheadedness, and/or constipation when reducing their calorie intake. However this program recommends a healthy balanced diet, rich in plant based foods, and a regular pattern of meals and snacks (consistent with national dietary recommendations), which may reduce this risk.

There are possible risks associated with the intervention activities, including the medical device, including:

Rare but serious (Event Rate < 1%): Potential to unmask heart disease

- Less Likely  $(1\% \le \text{Event Rate} < 5\%)$ : CGM site infection or tape allergy (<1-2%) (41)
- Likely  $(5\% \le \text{Event Rate} < 10\%)$ : sports injury such as ankle sprain, knee pain from increased physical activity.
- More likely (Event Rate  $\geq$  10%): None

There may be temporary discomfort with the device at insertion time. That can include bruising or redness of the skin, rare allergic reaction to the taped use to keep device in place, infection at site, and potential perceived dislike of having medical device on body for 10 days.

Participants may experience side effects from the fingerstick blood prick. There may be temporary discomfort including possible bruising or redness of the skin, lightheadedness, and on very rare occasion infection. People may experience embarrassment associated with measurements of weight and waist circumference. Minor discomfort may be experienced when answering questions that are personal in nature. Participants may have some lightheadedness or imbalance with the stair step test. Muscle strain or soreness are a rare risk of injury or joint discomfort with any the physical function tests. After demonstration by staff, if participants feel that the stair step test may be unsafe, they may choose not to do them.

There is a rare risk that a breach of confidentiality could occur; however, every effort is made to prevent this from happening. In addition, every effort is made to perform assessment activities in a private and respectful manner by research staff who have been specifically trained to do them.

#### G. **Benefits:**

Participants will likely receive no direct benefit from these measurements beyond receiving notification of their results. However, they may receive benefit from the lifestyle intervention activities. Participants may lose weight and/or reduce the level of one or more diabetes/heart disease risk factors if prediabetic and improve diabetes control if tjeuhave diabetes. This research may benefit society by enhancing our understanding of medical devices that may help improve lifestyle modifications and thus help establish new procedures and practices that are associated with reduced risk for diabetes and heart disease. This could also lead to improved health and well-being, and weight overall in adults.

### H. Conflicts Of Interest:

No conflicts of interest are noted.

### **I.** Confidentiality:

All of the subjects' personal information, clinical data and consent documents will be stored in a secure location in a locked file cabinet in the George Washington University Endocrine clinical research coordinator's office. The subjects' personal information and research related clinical data other than routine laboratory results will be accessible only to the Principal Investigator and the research staff associated with the study. Organizations that may inspect and copy your information include the IRB, The GeorgeWashington University. A master code linking the unique study numbers with subjects' identifying information will be kept by the Principal Investigator or by the Project Officer in a locked file cabinet. Additionally all data collected by coordinators will be entered and managed through the encrypted Research Electronic Data Capture (REDCap) system maintained at George Washington University/Children National Medical Center (CNMC). All data is deidentified with no personal health information entered (PHI). REDCap was developed specifically around HIPAA security guidelines. REDCap has been disseminated for local use at more than 940 other academic/non-profit consortium partners in 75 countries. REDCap servers are housed in a local data center at CNMC, and all web-based information transmission is encrypted. This system is accessed through a secure login and password. Only the RedCap database coordinators and study staff will have access privileges to the George Washington data set and will be strictly prohibited from sharing passwords. All will undergo the standardized authorized training provided by the RedCap team. Staff will maintain files in password-protected documents on HIPAA-compliant servers. REDCap programmers build in guality controls for the data that will be collected according to their stringent protocols. Data will be stored for 3 years after study completion for possible re-analysis and sub-group analysis that the clinical team may determine to be useful. More information about the consortium and system security can be found athttp://www.projectredcap.org. [name] and her research team will destroy the informed consent, research source documents, data files, and master code 3 years after the completion of the study. This will allow time for the PI and collaborators to reexamine the data as needed in the revision process for manuscripts submitted to peer-reviewed journals.

All information that the study subjects provide study personnel is for research purposes only and, as such, names and any other identifying information will not be reported or published in papers, presentations, or proposals that result from this research.

When the subject enrolls in the study, she/he will be assigned a unique study number that is not any part of his social security number or other personal identifier. These unique study numbers will be used to identify all information that subjects provide and any information that is collected from their medical records. The unique study numbers will be assigned sequentially according to the order of study enrollment and if they have diabetes (DM) or prediabetes (PDM). Subjects will be identified by the initials of the group to which they are randomized and 3 numbers according to their entry into the study beginning with 001. Therefore, the first subject randomized to the DM group will be DM-001 and the first subject randomized to the PDM group will be PDM-001. A total of 22 PDM and 23DM subjects will be enrolled.

Although every precaution is being taken to protect participant privacy, breach of confidentiality is always possible. In the unlikely event of a breach of confidentiality, the nature of the research data is not of a sufficiently personal nature to negatively affect employment status, lead to civil/criminal liability, incur financial risks to the study participants, or other risks.

### J. Subject Compensation:

Participants will be given \$25 upon completion of each visit and an additional \$50 dollars upon return of the CGM device at the end of study, for a total of \$150. Nutrition and exercise counseling sessions will be provided for free. Subjects will also have use of the medical device during the study for free. No additional cost will be incurred by subjects. Participants will be asked if they would like to receive additional information about alternative resources for weight loss in the community (Appendix G).

Title: A	Pilot Study on the Use of Real-Time Continuous G	ilucose Monitoring	(RT-CGM) as a	Tool for Weig	ht
Lo	ss/Behavior Modification in Patients with Prediab	etes and Diabetes			

NCT #: 03805412

Date: 18 November 2018

Initial statistical analysis

Sample Size Justification and data analysis: In order to establish stable estimates of effect sizes, we anticipate using a total sample size of N=30 patients (15 prediabetes, 15 Type 2 diabetes). Data will be analyzed using mixed model regression, which accounts for within subject correlation. The relevant effect size for each outcome will be the time main effect. As a secondary analysis, we plan to examine predictors of change using general linear models. This will help us determine the type of patient for whom the CGM intervention is most effective, which can inform the patient selection process in later studies. Predictors of interest include diagnosis (diabetes vs prediabetes), comorbidities, demographics (age, sex, race, type of insurance), BMI, and pre-intervention attitudes (toward diet, activity, and exercise changes)

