### **B. Background and Significance**

In the United States, more than 29 million people have diabetes and 86 million adults have prediabetes (1). Annual medical costs for persons with diagnosed diabetes average \$13,000, with approximately \$7,900 being directly attributable to the disease (2). Many comprehensive lifestyle intervention programs such as the Diabetes Prevention Program (DPP) (3) and behavior change strategies (alone or in combination) have been used to promote weight loss in obese, high-risk individuals with variable effects. These include motivational interviewing, accountability/self-monitoring programs, food journals (4-6), pedometers (7, 8) and mobile phone apps (9) for weight loss.

There is widespread acknowledgment that lifestyle behavior change is critical for weight and glucose regulation. The National Institute of Diabetes and Digestive and Kidney Diseases' DPP trial (3) demonstrated that lifestyle changes (diet and physical activity aimed at weight loss) were more effective than metformin in preventing diabetes among those with prediabetes (6); however, the DPP lifestyle intervention involved frequent visits and coaching over several years, which is costly and labor intensive. More scalable adaptations for community translation, such as a 12-session group-based program called Group Lifestyle Balance™ (GLB) have been shown to be effective in community settings. A recent meta-analysis conducted in 2012 reviewing 28 DPP translational interventions had an average weight loss of 4%. However, the attrition rate or drop-out rate was as high as 50% in some programs and weight loss was highly dependent on number of core sessions attended (10). In a pilot project that we just completed in conjunction with the George Washington Milken Instituteof Public Health with younger African-American women, the drop-out rate was 35% and participation mean was 5.5 (range 2-11) for the 12 core sessions and the need to evaluate alternative, self-directed behavior change

methods to promote weight loss. Thus, we propose to evaluate the utility of RT-CGM, an emerging technology that holds promise as a behavior modification tool to promote weight loss and lifestyle changes in those with obesity, prediabetes or diabetes.

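### The secondary predictor models use change scores, which by default lose anyone without a week 14 value; predictor-by-time terms in the planned mixed model would use every recorded weight

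*SAP*

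**What the plan says.** The SAP is one paragraph, headed Sample Size Justification and data analysis. Its main analysis reads "Data will be analyzed using mixed model regression, which accounts for within subject correlation", and the estimate of interest is defined by "The relevant effect size for each outcome will be the time main effect". For the secondary analysis, "we plan to examine predictors of change using general linear models". The predictors listed are diagnosis, comorbidities, demographics, BMI and pre-intervention attitudes, and the results are meant to guide patient selection in later studies. The SAP does not mention missing data, an estimation method, a covariance structure or a sensitivity analysis.

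The protocol (section D, Measurements) has weight taken at each visit, that is at weeks 0, 2, 6 and 14. HbA1c, lipids, the questionnaires and the step test are taken at baseline and week 14 only.

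On drop-out, Protocol section B says of published Diabetes Prevention Program translations that "the attrition rate or drop-out rate was as high as 50% in some programs" and that "weight loss was highly dependent on number of core sessions attended". Of the team's own earlier pilot it says "the drop-out rate was 35% and participation mean was 5.5 (range 2-11) for the 12 core sessions".

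**The concern.** The two analyses treat a participant who leaves before week 14 differently. The mixed model keeps that person's recorded weights. An ordinary general linear model of baseline-to-week-14 change has no outcome for that person and omits the record.

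If poorer responders are more likely to leave, two things follow in the change models. The mean loss among those who remain is too large. Predictor effects also shrink: more people are lost from the subgroup that responds less, and those who stay in it are its better responders, so the subgroups look more alike than they are. The second effect matters more here, because this analysis is meant to identify the type of patient who benefits most and to inform selection for later trials. The weights at weeks 2 and 6 that could reduce the problem will already have been collected.

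**Working it through.** **The plan's own figure.** There is none to reproduce. The SAP gives N = 30 (15 + 15) for stable effect-size estimates, without alpha, power, SD or drop-out.

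**Inputs.** From the protocol: the 4% average loss and the 35% and 50% drop-out figures, all from section B and all describing other programmes. Assumed: mean change -1.6% at week 6 and -4.0% at week 14; SD of week 14 change 5 points (range 3 to 7); week 6 SD 0.6 of that; correlation between week 6 and week 14 change 0.7 (range 0.5 to 0.85). Negative values are losses.

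**Step 1: mean change when everyone has a week 6 weight.** N = 30. A person leaves when 1.5 × (standardised change) + a standard normal deviate exceeds the cut-off that gives the stated drop-out.

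| Drop-out driven by | Drop-out | Completers | Likelihood model, unstructured | Random-intercept model |
|---|---|---|---|---|
| Nothing (random) | 35%, 50% | about -4.0 | about -4.0 | not run |
| Observed week 6 change | 35% | -5.65 | -4.00 | -4.9 |
| Observed week 6 change | 50% | -6.34 | -4.00 | -5.5 |
| Unseen week 14 change | 35% | -6.4 | -5.5 | -6.0 |
| Unseen week 14 change | 50% | -7.3 | -6.1 | -6.7 |

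Hand check of the second row: completers' bias = correlation × SD × [1.5/√(1.5² + 1)] × φ(z)/(1 - d) = 0.7 × 5 × 0.832 × (0.370/0.65) = 1.66, giving -5.66.

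Over the assumed ranges, the unstructured model's overstatement when leaving depends on the unseen week 14 change was about 0.5 to 2.8 points at 35% drop-out and 0.8 to 3.9 at 50%. It was about zero throughout when leaving depended on the week 6 change.

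**Step 2: leavers who go before week 6.** Under Weeks 2, 6 in the protocol, counselling starts at week 2, after a period of usual diet and activity. Week 6 is therefore the only interim weight that reflects response. With 35% drop-out driven by week 6 response (logistic, log-odds rising by 1.5 per SD of week 6 change), completers average -5.3. If half of the leavers go before week 6:

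- Completers' excess in week 6 SD units: 1.3/(0.7 × 5) = 0.37, so -0.37.
- Leavers must balance this: 0.37 × 0.65/0.35 = +0.69.
- Everyone with a week 6 weight: (0.65 × -0.37 + 0.175 × 0.69)/0.825 = -0.145.
- Likelihood estimate at week 14: -4.0 + 3.5 × (-0.145) = -4.5.

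With no early leavers the result is -4.0; if all leave early it is -5.3, the same as completers. Over the SD and correlation ranges the half-early result is -4.3 to -4.7. With half leaving early it is -4.35 at 20% drop-out and -4.2 at 10%.

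**Step 3: predictor effect.** Same set-up, adding a two-level predictor with a true week 14 effect of -3.0 points and 0.4 of that at week 6.

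| Analysis | Predictor effect |
|---|---|
| True value | -3.0 |
| Change model on completers | -2.7 |
| Predictor-by-time in likelihood model, week 6 seen | -3.0 |
| Same, half of leavers gone before week 6 | -2.9 |

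Attenuation is 0.3/3.0 = 10% in the change model and 0.1/3.0 = 3% in the mixed model with early leavers.

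**Step 4: bound for the mean.** All-participant mean = (1 - d) × completer mean + d × leaver mean. With completers at -4 and leavers at 0: 0.65 × -4 = -2.6 at 35%, and 0.50 × -4 = -2.0 at 50%. With leavers at -2: -3.3 and -3.0.

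**The case against.** The strongest reply is that the SAP already names a mixed model, and that a likelihood fit uses interim weights and is unbiased when leaving is predictable from them. Step 1 bears this out: the unstructured model returned -4.00 at both 35% and 50% drop-out driven by week 6 response. The reply stands for the primary analysis of weight, provided that the covariance structure is adequate and week 6 is observed. It does not cover the change models.

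A reader might infer several stronger points that the documents do not support:

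- *That the SAP specifies a complete-case analysis.* It does not use those words. Omission of leavers is the default behaviour of a general linear model of change, and it concerns the secondary analysis only.
- *That about a third of week 14 weights will be missing.* The drop-out figures describe other programmes; the 35% comes from a 12-session one. The protocol cites them to motivate a shorter, self-directed approach. This trial has four paid visits, and no drop-out is forecast.
- *That the background shows the mixed model's assumption fails.* A link between sessions attended and weight loss is equally compatible with leaving that is predictable from recorded weights.
- *That an arm comparison will be biased.* The SAP's estimate is the time main effect in N = 30. It contains no arm contrast.

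Sampling error also sets the scale. For a mean, the 95% half-width is 0.373 SD at n = 30 and 0.468 SD at n = 20; at SD 5 these are 1.9 and 2.3 points. A 0.3-point attenuation would not be visible in one trial of this size. That limits the urgency, but it does not favour the method that discards data.

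**Conclusion.** The point holds in a limited form. The change models in the secondary analysis are a weaker choice than the mixed model already planned, and the data needed for the better choice are collected anyway.

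Under an assumed 35% drop-out driven by week 6 response, change models on completers overstate mean loss by 1.3 points (5.3% against 4.0%) and attenuate a predictor effect by about 10%. The mixed model removes both errors if week 6 is seen, and most of both if half of the leavers go earlier (4.5%, and 3% attenuation). If leaving depends on unseen response, the mixed model is also biased, though less than completers. If leaving is random, neither is biased.

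All of these sizes rest on assumed SDs, correlations and drop-out mechanisms; none is a forecast for this trial. The documents do not support saying that the primary weight-loss estimate will be too large, only that it may be if leaving depends on unrecorded response, if many leave before week 6, or if the covariance structure is too simple. The last condition is open because the SAP does not state a structure.

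**What to change.** 1. Replace the general linear models of change with predictor-by-time terms in the same mixed model. Specify a likelihood-based fit, time as a category, unstructured covariance, and all recorded values from all enrolled participants. The predictor-by-week-14 term then gives the predictor's effect on change.
2. Add one sensitivity run for leavers: either a delta adjustment, or no change from baseline at week 14. Label it as a conservative bound and not as a correction.

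The cost is a few sentences of SAP text and one extra model run, with no new visits, measurements or participants. There are three limits. The no-change run understates loss when drop-out is unrelated to response: 2.6% for a true 4.0% at 35% drop-out, which is 1.4/4.0 = 35% too small. Outcomes taken only at baseline and week 14, such as HbA1c, lipids and the questionnaires, gain little, because a leaver has no interim value. An unstructured matrix over four visits has 4 × 5/2 = 10 parameters, so the SAP should name a fallback structure in case the model does not converge in a sample of this size.

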# **RESEARCH PLAN**

### A. Specific Aims

**Hypothesis:** We hypothesize that two sessions of 10 days of RT-CGM in the setting of nutrition and physical activity counseling coupled with education on how exercise and nutrition affect blood sugar levels will promote weight loss in participants with prediabetes and diabetes and reduce glycemic variability.

**Aim 1**: Examine the effect of two 10-day sessions of RT-CGM over 6 weeks on weight loss, change in body composition, activity level and nutritional changes in subjects with diabetes and prediabetes 12 weeks later.

Aim 2: Evaluate participants' perception of RT-CGM as a weight loss tool.

**Aim 3**: Evaluate the effect of RT-CGM on glycemic variability in subjects with prediabetes and diabetes.

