GW Medical Faculty Associates Internal Medicine clinic, Gynecology clinic, and Endocrine clinic by medical staff and provider flier (Appendix F). Information about the study will be made available to those patients by a Study Flier (Appendix H) which will provide them with contact information for the study coordinator. As well, if potential participants express interest in the study to medical staff at GW, permission for the study coordinator to contact them via telephone or email will be requested and potential participants will be contacted for further screening and potential enrollment. The Study Screening and research procedures will take place at the GW endocrine clinic. Subjects may also be identified through posters and flyers placed in the GW community. Potential subjects who satisfy the study criteria and express interest in the study will be given information about participation either by mail, email or a phone call, depending on their preference. Pre-screening questions will be asked but no study related procedure or screening questions will be performed until informed consent/authorization have been obtained (see Appendices D and L).

We propose to perform a prospective study of 45 participants that will involve 15 subjects (ages 18-55) who are obese (BMI>30) and have prediabetes with HbA1c 6.0-6.4%, and 15 obese (BMI>30) subjects with Type 2 diabetes (ages 18-55) and with HbA1c 7.0-10.0%. 15 subjects will be in the control group with either prediabetes (n=7) or diabetes (n=8). Subjects will be randomized to intervention or control through a computer-generated system. All eligible participants will be able to walk 2 city blocks at baseline. Patients with prediabetes will be on no medications for diabetes and patients with Type 2 diabetes will have to be on the same diabetes medication(s) for 3 months prior to enrollment. The medication regimen may include basal insulin but not premeal insulin. Uncontrolled diabetes A1c>10.1% will be excluded, as well as participants who are pregnant, lactating, enrolled in another weight loss program, or using a weight loss medication (see inclusion /exclusion criteria below). The study will be advertised by flyers in the GW Endocrine Clinic, Internal Medicine Clinic, and also advertisements in the local newspaper.

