#### Weeks 2, 6

RT-CGM education and use will be coupled to one initial nutrition and exercise counseling session at Week 2 by the diabetes educator. Individually administered nutrition and exercise counseling will be based on a condensed version of the standard 12-session Diabetes Prevention Program Group Lifestyle Balance (DPP GLB, Appendix B) material and received by all participants. All those enrolled in the CGM intervention (N=30) will participate in 2 cycles of RT-CGM with direct feedback on CGM patterns at the second session, Week 2.

Both groups will then follow up and be given diet and exercise education handouts and instruction based on the DPP GLB core nutrtion and physical activity materials (Appendix B) at Week 2. The diabetes and prediabetes CGM intervention groups will also receive additional education on how food and exercise affects bloods sugar, and how to evaluate and respond to their blood sugar changes with RT-CGM (Appendix A). The CGM intervention participants will then wear the RT-CGM device for 10 days at week 2 and at 6 weeks. At week 2, CGM patterns will be reviewed with diet and food logs, and CGM intervention patients will be challenged "to beat their averages. The control group will review their diet and exercise log with the instructor and attempt to continue to make small changes in diet and exercise. Vital signs will be taken at each visit, including waist circumference. Pedometer data will be collected at weeks 6 and 14. Week 2 education on nutrition and RT-CGM will take 1 hour 30 minutes to 2 hours. Week 6 CGM review and measurements will take 1 hour. They will mail their sensors back from the continuous glucose monitoring device after 10 days, along with physical activity and food logs. They continue wearing their pedometers during this time.

Page 8 of 14

#### Week 14

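### The SAP's effect size is change over time in 30 patients, so the randomised RT-CGM versus control comparison behind Aims 1 and 3 is never specified

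*SAP*

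**What the plan says.** The SAP is a single paragraph. On size, it says "we anticipate using a total sample size of N=30 patients (15 prediabetes, 15 Type 2 diabetes"). The reason given is stable estimation of effect sizes; no alpha, power, SD or drop-out allowance is stated. The model is a mixed regression allowing for within-subject correlation, and "The relevant effect size for each outcome will be the time main effect". A secondary analysis uses general linear models for predictors of change, with the purpose that "This will help us determine the type of patient for whom the CGM intervention is most effective". The listed predictors do not include randomised arm.

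The protocol describes a different design. Section D sets a maximum of 45 participants and says "Subjects will be randomized to intervention or control through a computer-generated system". It describes 15 with prediabetes and 15 with diabetes, and then "15 subjects will be in the control group with either prediabetes (n=7) or diabetes (n=8"). Under Weeks 2, 6: "All those enrolled in the CGM intervention (N=30) will participate in 2 cycles of RT-CGM". Section I (Confidentiality) gives 22 with prediabetes and 23 with diabetes.

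The condensed counselling is described under Weeks 2, 6 as "material and received by all participants". Aim 1 asks for the effect of two RT-CGM sessions on weight, body composition, activity and nutrition. Aim 3 reads "Evaluate the effect of RT-CGM on glycemic variability in subjects with prediabetes and diabetes".

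**The concern.** The two documents do not describe the same trial. The SAP's 15 + 15 matches the protocol's two RT-CGM groups, which leaves the 15 randomised controls with no stated role. The SAP does not say which 30 it means, and its text may predate the control arm.

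What separates the arms is RT-CGM and the teaching and feedback that go with it. Both arms receive the counselling, keep food and activity logs, wear pedometers and are set activity, fat and calorie goals with a 7% weight-loss target. Change over time reflects all of these. For glycaemic outcomes, selecting patients by HbA1c window may add some regression to the mean.

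Followed as written, the SAP could credit RT-CGM with change produced by the counselling and carry that into the later studies this pilot is meant to inform. The secondary analysis has the same gap: without controls it finds who changes, not who benefits from CGM.

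**Working it through.** **Inputs from the documents.** SAP: N = 15 + 15 = 30. Protocol section D: 15 + 15 RT-CGM and 7 + 8 control, so 30 + 15 = 45. Protocol section I: 22 + 23 = 45, which agrees with (15 + 7) + (15 + 8). The SAP's 30 is internally consistent but is not the protocol's total. It cannot be derived from a formula, because the SAP gives no inputs for one.

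**What each quantity estimates.** Let c be the mean change shared by both arms and δ the amount RT-CGM adds.

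- Time effect in the 30 RT-CGM patients: c + δ.
- Time effect pooled over 45, complete data, no arm term: (30(c + δ) + 15c)/45 = c + (2/3)δ.
- RT-CGM minus control: (c + δ) − c = δ.

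Only the third is the RT-CGM effect. Adding arm as a main effect would not be enough while time remains the effect size.

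**Precision**, as 95% CI half-width in SD of change, assuming complete data and equal SDs in the two arms. The two results in each row use normal and t quantiles; they are not an uncertainty range.

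| Quantity | Formula | Normal | t |
|---|---|---|---|
| Time effect, n = 30 | q/√30 | 0.358 | 0.373 (29 df) |
| Arm contrast, 30 vs 15 | q√(1/30 + 1/15) | 0.620 | 0.638 (43 df) |
| Same, stratified by diagnosis (15 vs 7, 15 vs 8) | inverse-variance | 0.620 | 0.638 (42 df) |
| Arm contrast, 20 vs 10 | q√(1/20 + 1/10) | 0.759 | 0.793 (28 df) |
| Arm-by-diagnosis | q√(1/15 + 1/15 + 1/7 + 1/8) | 1.241 | 1.279 (41 df) |

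The arm contrast is 0.638/0.373 = 1.71 times wider than the time effect. The 20 vs 10 row is a sensitivity case only. It borrows the 35% drop-out that protocol section B reports for another programme run by the team (45 × 0.65 = 29.25 completers).

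**Illustration, on assumed inputs.** Suppose δ = 0 and each outcome is tested two-sided at 0.05. Neither the test nor the shared changes below come from the documents. Paired-t power (noncentral t) for the time effect with n = 30:

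- c = 0.3 SD: 0.355
- c = 0.5 SD: 0.754
- c = 0.8 SD: 0.988

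A simulation of 20,000 trials at c = 0.5 SD gave 0.755 for the 30, 0.905 for all 45 pooled, and 0.051 for the between-arm contrast, which is its nominal level.

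**The case against.** The strongest defence is that this is a pilot. The SAP paragraph is labelled as an initial analysis, specifies no test and aims at estimation. The hypothesis in section A concerns RT-CGM given together with counselling, and a within-arm change can describe that package. This stands as far as it goes. It does not reach Aims 1 and 3, which name RT-CGM, and it leaves the randomised controls unused. A pilot may be imprecise, but it should estimate the quantity its aims name.

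The protocol's section letters skip E and K in the supplied text, so an arm comparison might have been described there. If so, the SAP would contradict it and would still need correcting.

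Some points properly limit the supporting evidence:

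- The shared change is unknown. In the team's earlier study (section C), 12-week HbA1c fell 0.5 with SMBG against 1.0 with RT-CGM, so a comparison arm can change. For weight in the same study, 9 SMBG patients lost and 12 gained more than 3 pounds, with 29 unchanged, which shows no net loss. That arm lacked this trial's counselling, so neither figure settles the matter here.
- Both HbA1c windows are bounded above and below, so the net direction of regression to the mean is unclear. Aim 3's variability measures were not selection criteria. The conclusion does not depend on this element.
- Baseline adjustment would narrow the contrast. Under equal variances the factor is √((1 + r)/2), giving about 0.54-0.55 SD at an assumed baseline-to-week-14 correlation r of 0.5. That is a reasonable alternative, and it is still a between-arm comparison.

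**Conclusion.** The concern holds and should be fixed before analysis. The SAP as written is wrong for this design, not merely brief: its N omits the control arm, and its effect size is c + δ (or c + (2/3)δ if pooled) where Aims 1 and 3 ask for δ. That conclusion follows from the allocation and the shared counselling alone and needs no numerical assumption.

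The loss of precision, from 0.36-0.37 to 0.62-0.64 SD, assumes unadjusted change scores, equal SDs and no drop-out. The false-attribution rates of about 36%, 75% and 99% are illustrations that depend on the assumed shared change and test. For the secondary analysis, a claim about who benefits from CGM would rest on contrasts as imprecise as 1.24-1.28 SD for diagnosis.

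**What to change.** Amend the SAP as follows.

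1. State the design as in the protocol: up to 45 randomised, 30 to RT-CGM (15 prediabetes, 15 diabetes) and 15 to control (7 and 8).
2. For each outcome measured in both arms, define the effect size as the RT-CGM minus control difference in change from week 0 to week 14, with its 95% CI. Estimate it from a mixed model of all randomised participants with arm, time, arm-by-time and diagnosis.
3. Report within-arm time effects descriptively, and likewise the week-14 CGM-perception questionnaire for Aim 2. The Measurements paragraph gives that questionnaire to the intervention group, while the Week 14 text is less clear about who completes it; settle this at the same time.
4. Replace the appeal to stability with the expected half-width of the contrast, about 0.62-0.64 SD of change at 30 vs 15. Show 0.76-0.79 SD at 20 vs 10 only as a drop-out sensitivity case.
5. Label the secondary analysis as exploratory predictors of change. For any statement about who benefits from CGM, use arm-by-predictor terms with CIs and state their low precision.

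The cost is SAP wording. Week-0 and week-14 measurements, including blinded CGM, are already planned in both arms, so no participants or visits are added. The downside is a less favourable, but relevant, statement of precision.
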